It is provided as a ready-to-use solution and is not typically diluted further. Pediatric doses will be drawn up by the pharmacy. Patients with SCD undergoing growth hormone stimulation test have tolerated 500mg/kg/dose over 30 minutes without complication. In practice, arginine infusion protocols are not typically modified for SCD. No complications with infusions were reported during the arginine trial recently published (1). Arginine compatibility is similar to that of total parenteral nutrition (TPN) and can be co-administered with normal saline/dextrose fluids, ketorolac, opioid analgesia/PCA and antibiotics. There are no issues with IV tubing, which can be changed according to CHOA policy. Although it is a hypertonic solution, the amount of fluid delivered with 1-2ml/kg is minimal and is not anticipated to trigger a pain crisis. In fact our data demonstrated that 1ml/kg of 10% Arginine-HCL given IV TID throughout hospitalization significantly decreased pain scores compared to placebo in children with SCD hospitalized for VOE (1). Past clinical trial experience with arginine did not support the need for a second IV placement specifically for the arginine infusion. Therefore, the clinical IV placed for parenteral opioid therapy will be utilized for study drug. If the IV site should become infiltrated, the IV catheter will be removed and the infiltration addressed clinically as needed, per hospital protocol for IV infiltration. A new IV catheter will be placed if the patient's clinical status mandates continued parenteral opioids or IV access is required for other reasons. If the patient loses his/her IV and it is no longer clinically needed, IV arginine will be discontinued per study protocol. Information on IV infiltration during arginine infusion will be collected and reported as an adverse event.

VOE resolution in patients discharged from the ED or day hospital/clinic and hospital will be defined as the time in hours, of study drug delivery to the time of the last parenteral opioid.

Length of Stay will be defined as the time in hours, of study drug delivery to the time that the discharge order is given in written or electronic form.

Pain Scores: Pain associated with VOE will be measured on a numeric pain rating scale of 0-10, with the ends representing the extreme limits of "no-pain" (0) and "worst pain" (10), or the FACES pain rating scale when appropriate. Pain scores will be obtained at presentation to the acute care setting for pain prior to study drug administration and at least TID daily, until discharge and at time of discharge.

Specific Aim 2: Safety monitoring

To monitor for potential toxicities associated with a loading dose & repeated administration of IV L-arginine.

Vital signs including blood pressure, hemoglobin, liver and renal function testing will be obtained at the same time as the study blood draw for research labs. Rates of acute chest syndrome, blood transfusion, clinical deterioration, need for intensive care and hospital/ED returns within 72 hours and 30 days will be monitored in all enrolled patients and compared between study arms.

Primary Outcome Measure: *The primary outcome measure is total parenteral opioid use (morphine equivalents mg/kg) calculated from the initial dose of study drug, throughout the ED and/or hospital stay in the arginine arms compared to placebo.*

Secondary Outcome Measures:

Clinical Outcomes

1. Length of hospital stay from study drug delivery to discharge (time of discharge order)
2. Time to VOE resolution after study drug delivery
3. Pain scores at presentation vs. discharge
4. Pain score over time
5. Length of ED stay (time of ED triage to discharge or admission order)
6. ED discharge rate
7. Total opioid dose (mg/kg) in the first 8 hours after study drug delivery
8. Number of study drug doses
9. Rate of acute chest syndrome (not present before randomization)
10. Rate of blood transfusion
11. Change in oxygen saturation and use of supplemental oxygen during admission. PROMIS pediatric Pain and Fatigue short forms (daily for up to 1st 7 days and then on day of discharge: collaboration with [name]/[name])
12. Symptoms questionnaire
13. 72-hour returns and 30-day return visits to the ED or in-patient hospitalizations
14. Diffusion correlation spectroscopy

Study Labs: Clinical, Research and Safety Monitoring

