Once informed consent is obtained, eligible children and adolescents age 3-21 years will be randomized to one of three study arms: Standard L-arginine dose (100 mg/kg IV TID), one-time L-arginine loading dose (200 mg/kg IV) + standard dose (100 mg/kg IV TID), or placebo (normal saline 1-2 ml/kg IV TID) up to a maximum of 7 days (21 doses) or until discharge, whichever comes first. The maximum loading dose of IV L-arginine will be 20 grams, with a standard dose maximum of 10 gms IV TID. A total of 114 patients will be treated/randomized in this protocol, 38 in each arm. Up to 150 patients may be enrolled, to account for potential screen failures and withdrawals. **Patients must be randomized within 24 hours of receiving their initial parenteral opioid in the ED or clinic/day hospital.** Even though a 24-hr window is established for feasibility, the ideal goal is to randomize and deliver study drug within 2-4 hours in the ED or clinic/day hospital. The average time to study drug delivery in the original [name] Arginine study was 20.4 ± 11 hours (1). Although this original study was not sufficiently powered to detect a decreased length of hospital stay (LOS), the trending decrease by 17 hours is a clinically relevant improvement for patients and their families. A standardized treatment and monitoring protocol for VOE utilized by Emory/Children's Healthcare of Atlanta mutually agreed upon by both the ED and department of hematology will be followed. Pain scores (0-10 scale or FACES as appropriate) will be obtained at presentation to the acute care setting for pain prior to study drug administration and at least TID until discharge. If the patient is discharged from the ED or day hospital/clinic without a hospital admission, a discharge pain score will also be obtained. A discharge blood draw will be obtained whenever possible for those discharged from the ED but will be limited to research labs targeting the arginine metabolome (plasma and erythrocyte amino acids, arginase activity, NO_x and exhaled NO). Information on hydroxyurea use (HU) will be obtained. Randomization will be stratified for HU use to minimize potential confounding effects of HU use. Patients,

physicians, and staff involved in patient care will be blinded as to whether each patient receives arginine vs. placebo.

Patients already participating in the clinical trial may not be enrolled more than once.

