A study binder will be kept by the research coordinator/enrollers that will record the names and unique identification code of each patient approached for enrollment in an enrollment log. The names and demographic information (age, gender, Hb-genotype) of those who were approached and decline enrollment and the reason for declining (if known) will be recorded as approached/not enrolled. Age, gender and Hb-genotype information on patients screened by the study team/coordinator but found to be not eligible will also be collected. All study binders will be kept in a locked cabinet in the research office of the PED or Aflac coordinators and electronic files with any private health information (PHI) will be kept in a password protected CHOA supported division sharepoint site that is backed up nightly. Only members of the study team will have access to the study folder.

Randomization and Arginine/Placebo Administration

Arginine/Placebo will be administered in a blinded fashion. Using randomization lists prepared by the

research pharmacist, the research pharmacist at Egleston Children's Hospital will perform a block randomization for all CHOA sites, and study drug will be allocated to the patient TID until discharge. **Randomization will be stratified for hydroxyurea use to insure an equal number of patients on HU in all arms to minimize this as a potential confounder.** The patient, nurses, and physicians caring for the patient will be blinded as to which medication the patient is receiving.

Once written informed consent is obtained, and eligibility is confirmed by study staff, children and adolescents age 3-21 years will be randomized to one of following three study arms:

- 1) Standard L-arginine dose (100mg/kg IV TID)
- 2) One-time L-arginine loading dose (200mg/kg IV) plus the standard dose (100mg/kg IV TID)
- 3) Placebo (normal saline 1-2 ml/kg IV TID)

Upon enrolment, the patient's medical record is reviewed for CMP and creatinine testing in the past month in the past 12 months.

- If there are no measurements within the past 12 months or if either SGPT/ALT or creatinine were elevated in the past 12 months (meeting exclusion criteria), the current CMP results must be reviewed prior to dose administration. (Patient may be randomized; however, delivery of study drug should be held until CMP results are reviewed and no exclusion criteria are noted).

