The primary goal of this analysis is to compare the standard arginine treatment with placebo. The power analysis is based on this comparison. This sample size calculation is based on a two-sample two-sided t-test, with the objective of detecting a 55% reduction in opioid use from its mean value (4.1) in the placebo group based on the preliminary data generated from the recent [name] arginine trial (1). Based on these findings, the standard deviations are 2.0 and 4.1 (days) in the arginine and the placebo groups, respectively. A sample size of 33 subjects per group has 80% power to detect the treatment effect stated above on a two-sided test at the 0.05 significance level. A secondary goal is to compare the other arginine treatment arm (with a loading dose) to the placebo arm. Finally the two arginine treatments will be compared to determine if there is any difference or trend towards a difference when a loading dose is used that is superior to the standard arginine dose used with success in prior studies. Based on past experiences with arginine therapy, few patients withdrew from the study after the therapy was switched from oral to parenteral. Up to 150 patients will be enrolled, allowing for screen failures and study withdrawal, in order to insure randomization and study completion of 108 patients (36 per group) allowing for a 7% withdrawal rate. We did not adjust the sample size calculations for multiple comparisons as the power calculation only corresponds to the primary goal involving a single comparison of patients receiving the standard treatment or the placebo. We anticipate that the "loading dose" arm will be either the same or better than the standard dose. We will evaluate the efficacy and safety of this loading dose compared to the placebo group.

Each of the comparisons mentioned above will be conducted via a general linear model analysis. Predictors will include the treatment indicator, use of HU, age group, gender and the interactions of each of the last three covariates with the treatment indicator. By including interactions in the model we will be able to determine whether the treatment effect varies across subgroups of patients.

Assistance with statistical analysis and power calculation was provided by the Department of Biostatistics and Bioinformatics at the Rollins School of Public Health, Emory University, by [name] PhD, who will be the biostatistical consultant on this project.

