Sample size power analysis for LOS as outcome: Goal for a future phase 3 RCT

This proposal will help provide more accurate data to generate a sample size power analysis for decreased LOS as the primary outcome measure in a multi-center Phase 3 RCT in the future.

If the true difference (based on the [name] et al (1)) between groups were 17 hours for LOS, n=150 subjects would be required in each group to have 80% power to detect a difference, assuming a 5% type 1 error rate and estimated standard deviation of ~ 50 hours. Given > 20 hour delay in administration of study drug from time from ED presentation for most patients in the [name] study (1), study drug administration within < 12 hours of ED presentation (ideally < 4 hours) will improve our power to detect a difference in LOS, likely requiring a smaller sample size. See below calculations and **Figure 11**. If the true decrease in LOS were closer to 24 hours (theoretically achievable with the elimination of delay in study drug delivery), a sample size of 76 patients in each group (n=152 total) is needed, approximately half the size required based on our current data. This proposed study is therefore a sound investment to insure the best design for a future phase 3 trial that will advance this orphan drug towards FDA regulatory approval.

Two-Sample T-Test Power Analysis

Numeric Results for Two-Sample T-Test

Null Hypothesis: Mean1=Mean2. Alternative Hypothesis: Mean1≠Mean2

The standard deviations were assumed to be unknown and unequal.

Allocation									
Power	N1	N2	Ratio	Alpha	Beta	Mean1	Mean2	S1	S2
0.80251	150	150	1.000	0.05000	0.19749	0.0	17.0	43.0	60.0
0.80277	134	134	1.000	0.05000	0.19723	0.0	18.0	43.0	60.0
0.80154	120	120	1.000	0.05000	0.19846	0.0	19.0	43.0	60.0
0.80007	108	108	1.000	0.05000	0.19993	0.0	20.0	43.0	60.0
0.80385	99	99	1.000	0.05000	0.19615	0.0	21.0	43.0	60.0
0.80254	90	90	1.000	0.05000	0.19746	0.0	22.0	43.0	60.0
0.80045	82	82	1.000	0.05000	0.19955	0.0	23.0	43.0	60.0
0.80361	76	76	1.000	0.05000	0.19639	0.0	24.0	43.0	60.0

Power Analysis Summary Statements

Group sample sizes of 150 and 150 achieve 80% power to detect a difference of -17.0 between the null hypothesis that both group means are 0.0 and the alternative hypothesis that the mean of group 2 is 17.0 with estimated group standard deviations of 43.0 and 60.0 and with a significance level (alpha) of 0.05000 using a two-sided two-sample t-test.

Site Monitoring Plan

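### The primary model adjusts for no measure of opioid need before randomisation, so the comparison is unbiased but may be less precise than the charted data allow

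*Combined protocol and SAP*

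**What the plan says.** **Entry window.** Specific Aim 1: Efficacy sets the limit: "Patients must be randomized within 24 hours of receiving their initial parenteral opioid in the ED or clinic/day hospital". The same paragraph gives a target that is not a rule: "the ideal goal is to randomize and deliver study drug within 2-4 hours in the ED or clinic/day hospital".

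**Start of drug.** The limit applies to randomisation, not to the first infusion. Under Randomization and Arginine/Placebo Administration, patients with no chemistry in the past 12 months, or with raised values in that time, may be randomised, but "delivery of study drug should be held until CMP results are reviewed and no exclusion criteria are noted". No time limit is given for that hold.

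**Outcome.** The Primary Outcome Measure is total parenteral opioid in morphine equivalents mg/kg, "calculated from the initial dose of study drug, throughout the ED and/or hospital stay". The Abstract describes opioid use over the whole ED visit and hospital stay. The two should be reconciled; this point follows the Primary Outcome Measure.

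**Model and stratification.** Statistical Analysis specifies a general linear model: "Predictors will include the treatment indicator, use of HU, age group, gender and the interactions of each of the last three covariates" with treatment. Stratification is by hydroxyurea only: "Randomization will be stratified for HU use to minimize potential confounding effects of HU use". No section adjusts for or stratifies by opioid already received, time since first opioid, or baseline pain.

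**Data available.** The time of the first parenteral opioid is needed to apply the window. Monitoring During Study has nursing staff document parenteral opioids every shift and provides for a chart review.

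**The concern.** Every patient has had parenteral opioid before entry, in an amount and over a period that vary between patients. Someone randomised a few hours into ED care and someone randomised close to 24 hours are at different stages when counting starts. How much opioid a child has already needed, and over how long, may predict how much more will be needed. If so, a model without that information leaves explainable variation in the residual and gives a wider interval than necessary.

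The stake is the width of the interval around the main efficacy estimate. Planned power is modest (33 per group for 80%), the placebo standard deviation is as large as the placebo mean, and the added covariates would need no further patients.

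**Working it through.** **Inputs from the documents.** Placebo mean 4.1 mg/kg; target reduction 55%; SDs 2.0 (arginine) and 4.1 (placebo); two-sided alpha 0.05; 33 per group for 80% power; 36 per group as the completion target, with 7% withdrawal (all Statistical Analysis). The SDs are labelled as days there, but the pilot's SEMs of 0.4 and 0.8 mg/kg with n = 26 give 0.4 × √26 = 2.04 and 0.8 × √26 = 4.08, so mg/kg is meant. From the pilot results: placebo stay 4.8 days; time to drug 20.4 h, SD 11 h.

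**1. Reproduce the plan's figure.**
- Difference = 0.55 × 4.1 = 2.255 mg/kg.
- Root-mean-square SD = √((2.0² + 4.1²)/2) = 3.226.
- Normal approximation: n = 2 × (1.960 + 0.842)² × 3.226² / 2.255² = 32.1, so 33. This matches.
- 33 / 0.93 = 35.5, so 36.
- Welch power (noncentral t) is 79.4% at 33 and 82.9% at 36 per arm.

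**2. Effect of adjustment.** If the added covariates have combined correlation r with the outcome, beyond the terms already in the model, each residual SD is multiplied by √(1 − r²). At r = 0 the 95% half-width with 36 per arm is 1.96 × √((2.0² + 4.1²)/36) = 1.49 mg/kg. The documents give no r, so a range is assumed, taken as equal in both arms:

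| r (assumed) | Power, 36 per arm | 95% half-width, mg/kg | n per arm for 80% (normal approx.) |
|---|---|---|---|
| 0 | 82.9% | 1.49 | 33 |
| 0.2 | 84.4% | 1.46 | 31 |
| 0.3 | 86.2% | 1.42 | 30 |
| 0.4 | 88.8% | 1.37 | 27 |
| 0.5 | 91.9% | 1.29 | 25 |
| 0.6 | 95.3% | 1.19 | 21 |

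**3. How much delay alone could explain.** Average pilot placebo rate = 4.1 / (4.8 × 24) = 0.0356 mg/kg/h. Variance share = (rate × SD of delay)² / 4.1². A rate three times the average is an assumed case for heavier early use.

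| Spread of start times | Average rate | Three times the average rate |
|---|---|---|
| Even over 0–24 h (SD 24/√12 = 6.9 h) | 0.4% | 3.3% |
| SD 11 h, as in the pilot | 0.9% | 8.2% |

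These shares correspond to correlations of about 0.06 to 0.29 (square roots of 0.0036 and 0.082). The middle and top of the range in step 2 would therefore have to come from prior opioid as a marker of severity.

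**4. Whether a treatment-by-delay test could be informative.** Take two arms of 36, each split evenly into early and late starters. The SE of the difference between the two treatment effects is twice the overall SE: 2 × √(20.81/36) = 1.52 mg/kg. Normal-approximation power is about 11% if the effects differ by half the planned effect (1.13 mg/kg) and about 32% if they differ by all of it (2.255 mg/kg).

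**The case against.** **This is a refinement, not an error.** Both quantities precede randomisation, so they are balanced in expectation. The planned comparison is unbiased, and 36 completers per arm already exceed 80% power on the plan's own assumptions. That stands, and the point is confined to precision.

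**The gain is assumed.** No section reports how pre-randomisation opioid relates to later use. With drug given near the 2–4 hour target under a standardised pain protocol, prior opioid may reflect a few protocol-driven doses and predict little. It is also a total over a period that differs by patient, not a true baseline value of the outcome. This stands too; it is why the result is a range and why time since first opioid should accompany the opioid total. The pilot's correlation of 0.86 between opioid use and length of stay does not supply the missing figure, because both were measured over the stay rather than before randomisation.

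**Stronger readings a reader might infer:**
- *That delay moves the outcome by a large part of the planned effect.* Multiplying the average rate by the full window gives 0.0356 × 24 = 0.85 mg/kg, which looks large beside 2.255. But that contrasts two individual patients at opposite ends of the window, whereas 2.255 is a difference between arm means. Delay does not differ systematically between arms.
- *That drug start is bounded at 24 hours, or that the window simply repeats the pilot's delay.* The limit is on randomisation. The pilot's 20.4 hours ran from triage or presentation, not from first opioid, so the two clocks differ.
- *That the trial fails to test its own reason for dosing early.* The section on length of stay as an outcome does say "study drug administration within < 12 hours of ED presentation (ideally < 4 hours) will improve our power to detect a difference in LOS", but it concerns a future phase 3 trial. The Specific Aims contain no timing question.

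**Conclusion.** The point holds as one of precision. Counting begins at a variable stage of the crisis and the model carries no measure of opioid need up to that stage. The treatment comparison remains valid without one. With 36 per arm, adjustment would raise power from 82.9% to somewhere between 84.4% and 95.3% for an assumed combined correlation of 0.2 to 0.6, and would narrow the 95% half-width from 1.49 to between 1.46 and 1.19 mg/kg. With a correlation near zero there is essentially no gain. These figures rest on the plan's effect and SDs, on the same correlation in both arms, and on that correlation being additional to hydroxyurea, age group and gender.

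Delay by itself probably contributes little. A treatment-by-delay analysis cannot settle whether earlier dosing works better: delay is not randomised, it may track severity or ED conditions, and power is about 11% to 32% in the cases shown.

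**What to change.** In the general linear model under Statistical Analysis, prespecify before unblinding two baseline covariates as main effects:

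1. parenteral opioid given before randomisation, in morphine equivalents mg/kg, with the same conversion as the primary outcome;
2. hours from first parenteral opioid to randomisation.

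Both should stop at randomisation rather than first infusion, so that any hold for laboratory review does not bring post-randomisation time into a baseline covariate.

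If a treatment-by-delay estimate is reported, label it exploratory, give it with its confidence interval, and do not use it to set the length-of-stay assumption for phase 3.

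The cost is a change of analysis wording, two degrees of freedom, and abstraction of timed opioid doses before randomisation from the medication record. The entry window, patient numbers, visits and procedures are unaffected.

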- Hemoglobin less than 5 gm/dL or immediate need for red cell transfusion anticipated within the next 12 hours.
- Hepatic dysfunction: SGPT (ALT) > 3X upper value
- Renal dysfunction: Creatinine >1.0
- Mental status or neurological changes
- Acute stroke or clinical concern for stroke
- Pregnancy
- Allergy to arginine
- Two (2) or more ED visits within the last 7 days prior to CURRENT ED visit
- Hospital discharge < 14 days prior to presentation to ER.
- Previous randomization in this arginine RCT (patient consented and screen failed before receiving study drug or placebo remains eligible for future participation).
- Patient refusal
- Use of inhaled nitric oxide, sildenafil or arginine within the last month
- Acidosis with CO₂ ≤ 16
- Hypotension requiring treatment with clinical intervention
- Not an appropriate candidate in the investigator's judgement
- Newly started on HU for < 3 months
- PICU admission from the emergency department

Patients will be given or sent electronically a standard consent form prior to study enrollment approved by the institutional review board (IRB). This consent form will provide a brief summary of the study protocol and will provide families with contact information for the principle investigator and IRB personnel should they have any questions/concerns about the study. Both informed parental consent and patient assent, where appropriate, will be obtained electronically, and when appropriate a paper consent can be obtained. A copy of the consent and assent, where appropriate, will be placed in the patient's medical chart. If a copy of the consent form is sent electronically to a patient, this will be sent either via REDCap or via encrypted email, as such the patient's electronic mailing address will be captured.

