- If CMP and creatinine levels were normal enough to not meet exclusion criteria in the past 12 months, the patient can receive the first dose of study drug and the CMP and creatinine labs reviewed when available.
- Patients with a CMP after randomization that meet exclusion criteria will have study drug stopped for toxicity monitoring. With an intention-to-treat analysis, these patients will remain on study. Blood analysis and exhaled NO_x measurements will continue per protocol, but arginine/placebo supplementation will be terminated.

Administration of Analgesics to Study Patients

Patient Controlled Analgesia (PCA) devices will be used in admitted patients whenever possible according to standard practice at CHOA. Intravenous ketorolac, oral NSAIDS and oral opioids with acetaminophen may be used in addition to parenteral opioids. Intranasal fentanyl may be administered at presentation in the ED per protocol. Dosing of the PCA will follow a standard protocol of pain management established by the Aflac sickle cell center.

Monitoring During Study

Patients will be identified from the over 1400 ED SCD patient visits/year for VOE in children followed by the staff at the Aflac Sickle Cell Center of CHOA/Emory University School of Medical. They will be examined daily by the clinical team and will undergo routine vital signs including blood pressure per clinical protocol. A chart review will be performed, and pertinent data extracted. A pain score will be obtained and recorded daily (at least 3 times a day, once per shift) and at time of discharge. Standard of care pain scores will be utilized. A symptom questionnaire to assess for potential side effects of arginine will be completed daily by the study coordinator (see appendix). Information for the symptom's questionnaire evaluating for potential adverse events should be obtained by direct questioning of the patient/family in addition to the medical record. Use of parenteral narcotics will be documented every shift by nursing staff per standard protocol and will include narcotics delivered by the PCA device as well as any additional intravenous, intranasal and/or oral opioids used. Data on total daily opioid use will be collected by study team coordinator.

Laboratory monitoring will be undertaken according to the schedule below:

	DAY 0	DAY 1	Day 7/Discharge*
CBC with retic count (SOC)	X	X	X
Comprehensive metabolic panel	X	X	X
Urinalysis for protein (urine to Brown lab)	X	X	X
BHCG (girls > 12 yrs)	X		

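### Time to VOE resolution goes negative when no parenteral opioid follows the first study dose; the plan needs a 0-hour rule, and a rule for patients randomised but never dosed

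*Combined protocol and SAP*

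**What the plan says.** All three clocks start at study drug. In the study design section under Specific Aim 1, VOE resolution, for patients discharged from the ED, the day hospital or clinic, or the ward, "will be defined as the time in hours, of study drug delivery to the time of the last parenteral opioid". In the same place: "Length of Stay will be defined as the time in hours, of study drug delivery to the time that the discharge order is given". The Primary Outcome Measure is parenteral opioid use "calculated from the initial dose of study drug, throughout the ED and/or hospital stay in the arginine arms compared to placebo".

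The entry window is set from a different event: "Patients must be randomized within 24 hours of receiving their initial parenteral opioid in the ED or clinic/day hospital". Delivery of study drug within 2 to 4 hours is given as a goal and not as a limit.

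On patients who may not be dosed, the section Randomization and Arginine/Placebo Administration says, for those without recent acceptable laboratory results: "Patient may be randomized; however, delivery of study drug should be held until CMP results are reviewed and no exclusion criteria are noted". A later bullet covers patients whose metabolic panel after randomisation meets exclusion criteria. Their study drug is stopped, and the text adds: "With an intention-to-treat analysis, these patients will remain on study". Specific Aim 1 counts the 114 patients as treated/randomized, as if these were one set. The Exclusion Criteria bar previous randomisation but add in parentheses: "patient consented and screen failed before receiving study drug or placebo remains eligible for future participation". The Statistical Analysis section defines no analysis set and gives no rule for either situation.

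**The concern.** VOE resolution is a duration, so it should not fall below zero. Under the stated definition it does so whenever the last parenteral opioid came before study drug. Within that group the score reflects only events before treatment: for a fixed last-opioid time, each hour of delay in delivering study drug makes resolution look one hour faster. Whether a child needs opioid after the first dose can depend on treatment, so the number of such scores may differ between arms, and pre-dose timing then enters the comparison.

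The second issue concerns who is analysed. A patient randomised with drug on hold, whose panel then meets an exclusion criterion, is never dosed. With no dose there is no starting time for any of the three outcomes. If the rule is left until the data are seen, the choice of who counts is made late, in arms of only 38.

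**Working it through.** **Can the time be negative?** VOE resolution = time of last parenteral opioid − time of study drug, reading delivery as first delivery. The entry text was checked for anything that forces the result to be positive:

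- Specific Aim 1 describes eligible children as receiving parenteral opioids. The Inclusion Criteria require moderate-to-severe pain treated with them. Neither asks for a continuing need at the first study dose.
- The 24-hour window runs from the first parenteral opioid to randomisation, and delivery itself has no limit.
- Administration of Analgesics to Study Patients allows ketorolac, oral NSAIDs and oral opioids alongside, so parenteral treatment can end while pain treatment goes on.
- The Exclusion Criteria remove children with a decision to discharge home. This lowers the frequency but does not bring it to zero.

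Illustrative times, all assumed, in hours from the first parenteral opioid:

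| Last parenteral opioid | Study drug | VOE resolution |
|---|---|---|
| 1 | 3 | 1 − 3 = −2 |
| 1 | 4 | 1 − 4 = −3 |
| 2 | 12 | 2 − 12 = −10 |
| 6 | 4 | 6 − 4 = +2 |

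The first two rows match the protocol's 2-to-4-hour goal. The third needs a long gap without parenteral opioid in a child who still qualifies, and is a corner case.

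**Effect on the other outcomes.** In the negative rows no parenteral opioid follows study drug, so the primary outcome is 0 mg/kg. The discharge order comes after study drug, so length of stay is positive.

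**Effect on an arm mean.** Compared with a 0-hour rule, k patients at −h hours among 38 move the mean by −k × h / 38. The documents give neither k nor h. Assuming 5 to 10% of 38 (1.9 to 3.8, so 2 to 4 patients):

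- 2 patients at −2 h: −4/38 = −0.11 h
- 4 patients at −3 h: −12/38 = −0.32 h
- 4 patients at −10 h (corner case): −40/38 = −1.05 h

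The between-arm effect is the difference of two such shifts. For example, 4 patients in one arm against 2 in the other, all at −3 h, gives (12 − 6)/38 = 0.16 h.

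**Never-dosed patients and power.** The plan's own figure comes first. Difference = 0.55 × 4.1 = 2.255 mg/kg. Root-mean-square SD = √((2.0² + 4.1²)/2) = 3.226. The normal approximation, 2 × (1.96 + 0.84)² × 3.226² / 2.255², rounds up to 33 per group, as stated. The unequal-variance t-test gives 79.4% power at 33. With the same test and the planned 38 per arm:

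| Without a primary value, per arm (assumed) | Analysed | Power |
|---|---|---|
| 0 | 38 | 84.9% |
| 2 | 36 | 82.9% |
| 3 | 35 | 81.8% |
| 5 | 33 | 79.4% |

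The loss is small. The difficulty is one of definition: without a dose, all three outcomes lack a start.

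**The case against.** The case against has weight. Eligible children are described as receiving parenteral opioids, in the present tense. They have moderate-to-severe pain, those about to go home are excluded, PCA is used in admitted patients whenever possible, and study drug goes through the IV placed for opioid therapy. A child with no parenteral opioid for many hours before study drug fits this picture poorly. The list of Secondary Outcome Measures also describes the time as running after study drug delivery, which makes 0 hours a natural reading when no opioid follows. The planned model is a general linear model, with no survival method named, so a few small negative values would not break it. All of this limits frequency and size, and it stands. It does not replace the working definition under Specific Aim 1, which expressly covers ED and clinic discharges and has no floor.

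On never-dosed patients, the intention-to-treat sentence sits beside wording about stopping study drug, which suits patients already dosed. The treated/randomized count and the Exclusion Criteria parenthesis lean towards a dosed population. The hold for laboratory results is also blinded and comes before dosing, so losses by that route should not depend on arm. This too stands: the text is unsettled between two populations, and no bias is shown.

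**Conclusion.** The definition of VOE resolution needs correcting. As written it can return negative times, plausibly of a few hours and mainly in ED or clinic discharges. On assumed frequencies the effect on an arm mean is a fraction of an hour. The never-dosed patient is a secondary point of reconciliation.

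A reader might infer more, and the documents do not support it:

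- **That all three outcomes are distorted in dosed patients.** In dosed patients only VOE resolution goes negative. The other two lack a value only when no dose was given.
- **That values near −10 or −24 hours are typical.** The text does not exclude them, but they need long gaps that sit badly with entry on active parenteral treatment and a 2-to-4-hour goal.
- **That the plan plainly breaks its own intention-to-treat analysis or biases the comparison.** The single mention of intention-to-treat can be read as covering dosed patients, and the blinded hold gives no route to arm-dependent loss.
- **That one child may be counted in two arms.** The main clause on previous randomisation, and the statement under Specific Aim 1 that participants may not be enrolled more than once, both bar this. What remains is an ambiguity: a child allocated but not dosed could be thought to fit the parenthesis.

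Every frequency used here is an assumption, since the documents report none.

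**What to change.** 1. **VOE resolution.** State that the time runs from the first delivery of study drug and is set to 0 hours when no parenteral opioid is given after it. The primary outcome needs no added rule, as it is already 0 mg/kg.

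2. **Never-dosed patients.** Choose one option and write it into Statistical Analysis. (a) Use randomisation as the time origin for every patient and outcome, analyse all randomised patients, and state the 0-hour rule from that origin. The cost is that opioid given between randomisation and first dose enters the primary outcome and dilutes the effect slightly. (b) Keep the present clocks, name a randomised-and-dosed analysis set, and report the number never dosed by arm. The cost is giving up the intention-to-treat label for that analysis. Starting at randomisation for never-dosed patients and at study drug for the rest would mix two origins within an arm and should be avoided.

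3. **Repeat entry.** Reconcile the Exclusion Criteria parenthesis with its main clause and with Specific Aim 1, so that screen failed means failed before randomisation.

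This is a few sentences of wording, settled before unblinding. It needs no new patients and no change to the stated sample size or power.
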